11.3 Health Economic Assessment

The economic assessment will include a comparative analysis of outcomes and costs between the current, predominantly emergency care-based, and new, with specialist unit-based, models of care and the assessment of the cost-effectiveness of the new model of care for acute sickle pain. This entails measurement, valuation and comparison of outcomes and costs of the two alternative care pathways to treat acute sickle pain. The evaluation will be performed from the NHS and personal social services (PSS) perspective as reference case²⁰ with additional analysis from the societal perspective.

11.3.1 Assessment of outcomes

Two outcomes, namely pain and health-related quality of life, will be used in the evaluation. These measures are among core outcomes identified for use in clinical trials of SCD interventions.²¹ Pain during the first 6h is the primary clinical outcome in the trial. Effective pain management is expected to improve patient's quality of life (QoL).²² Previous studies among patients hospitalised for acute sickle pain have shown a reduction in pain and an improvement in quality of life post treatment and discharge.^{23, 24} Data on QoL will be assessed using the EQ-5D five level (EQ-5D-5L) instrument, administered to patients at initial consent, at baseline, 6 hours, 14 days and 28 days follow up. Responses to the EQ-5D will be used to calculate patient QoL utilities²⁵ at particular points of time by applying the UK population tariff and their quality adjusted life years (QALY) over follow-up periods using area under the curve approach.

In addition to patient related outcomes, we aim to assess care provider's quality of life outcomes. We will identify primary care giver for patients, administer EQ-5D questionnaire and estimate QALY for care givers.

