6.4 Secondary endpoints

- Time to first analgesia, defined as time from presentation in ACU or ED to first dose of opioid analgesia administered. (For subjects given parenteral opioid prior to arrival in care unit, e.g. in ambulance, timing will start from one hour after parenteral analgesia given in ambulance, even if subject presents less than one hour after analgesia given in ambulance)
- Adherence to NICE guideline in safety observations (defined as proportion of hourly safety observations (respiratory rate, sedation score) taken within first 6 hours (+/- 30 mins)
- Adherence to care plan in analgesia doses (defined as proportion of analgesia doses given according to protocol within first 6 hours (+/- 30 minutes)
- Fit for discharge by 6 hours after first analgesia (defined as pain score 5 or less for at least 2 consecutive hourly assessments; no requirement for parenteral opioid for at least 2 hours and acceptable oral analgesia protocol available for use at home, NEWS score green for >2 hours, patient able to self-administer oral medication, patient mobile. All the above assessed by physician and agreed with patient)
- Time from first analgesia to fit for discharge (defined as pain score 5 or less for at least 2 consecutive assessments; no requirement for parenteral opioid for at least 2 hours and acceptable oral analgesia protocol available for use at home, NEWS score green for >2 hours, patient able to self-administer oral medication, patient mobile. All the above assessed by physician and patient).
- Cumulative dose of morphine or equivalent opioids in first 6 hours and first 24 hours
- Proportion admitted to hospital from ACU or ED
- Length of hospital stay (for those admitted to hospital), length of hospital stay Patient satisfaction with care assessed using SCAPE questionnaire 14 and 28 days after discharge
- Health economic analyses of comparative patient health-related quality of life, costs and cost-effectiveness of ACU versus ED care from the perspective/s of health and social care (NHS and PSS) and, separately, wider society
 - Costs at 28 days post-randomisation
 - QALY at 28 days post-randomisation
 - Incremental cost-effectiveness ratio

7. Study population

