Patients will not be randomised if:

1. Pain can be managed without the need for hospital attendance.

2. Symptoms suggest a complicated crisis, where additional medical problems need to be managed.

3. ACU is not available at the trial centre.

The procedure for these different eventualities is illustrated in the flow-chart (Appendix 3).

Randomised patients

For randomised patients, their management will be implemented by their health care team for ED or ACU, using their pre-agreed pain management protocol. The trial team will not be responsible for treating the patient, but will have the following responsibilities:

- Confirmation of consent, eligibility and allocation to correct treatment location
- Pain score (0-10 numeric rating scale) at baseline and hourly for first 6 hours
- Collection of the following data:
 - a) Safety data (respiratory rate and sedation score) hourly for first 6 hours (taken from hospital paper or electronic record. Record actual values and percentage of scheduled measurements.
 - b) Adherence to pre-agreed pain management protocol.
 - c) Cumulative opioid dose over the first six hours (from hospital paper drug chart or electronic prescribing record) and duration of episode in ED or ACU (APC episode resource use CRF).
 - d) Whether the patient is admitted or discharged from ED or ACU.
 - e) Any additional analgesic medication and all non-analgesic medication.
 - f) Health economic data (Section 11.3)

- g) Patient satisfaction questionnaire, taken 14 and 28 days after presentation using the SCAPE questionnaire.
- h) Quality of life assessment; using the EQ-5D-5L tool taken on consent, presentation, 6 hours, 14 and 28 days after the presentation.
- i) Length of stay for patients admitted to hospital. Defined as time from the decision to admit, to time patient leaves ward.
- j) Re-attendance rate (within 7 days).
- k) Complication rate (acute chest syndrome, other acute sickle complications, physician diagnosis from discharge summary).
- I) Education/employment/daily activity loss (social determinants of health assessment).
- m) Resource use CRF including Work Productivity and Activity Impairment Questionnaire, collected at consent, 14 days and 28 days follow-up.

Observational Arm

Consented subject may be triaged with an uncomplicated APC, but cannot be randomised for a number of reasons including:

- No trial staff available
- No available space on ACU
- ACU is closed
- Presenting within 6 hours of closure of ACU

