These subjects will be managed according to normal standard care. The trial team will be responsible for a phone call 14 and 28 days after presentation and will collect clinical data the following data:

- Analgesic medication and all non-analgesic medication (from hospital paper drug chart or electronic prescribing record) and duration of episode in ED or ACU (APC episode resource use CRF).
- Quality of life assessment; using the EQ-5D-5L tool taken on consent, presentation, 6 hours and 7, 14 and 28 days after the presentation.
- Education/employment/daily activity loss (social determinants of health assessment).
- Resource use CRF including Work Productivity and Activity Impairment Questionnaire, collected at consent, 14 days and 28 days follow-up.
- Length of hospital admission, if applicable.
- Adverse events (recorded in the clinical notes and discharge summary).

9. Study procedures

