9.6 Schedule of Assessment

See Table 1.

Study event	Screening	Consent and enrollment	Phone triage with APC	ED or ACU with APC	Discharge	Follow up	Follow up						
Study Day			1		1							1.1 douro	20. devie
Study event number	4				1	1	-			10	14	14 days	26 days
	1	4	2 3	4	5	6				10	11	12	13
Study time (nours)				(1	2	: 3	4	+ t	6			
Eligibility	X												
Confirm individual protocol		х	х	х									1
Given patient information sheet	х												1
Informed consent		х											1
Confirm consent			Х										
Demographics ^b		Х											
Medical history ^c		Х	Х										
Confirm inclusion/exclusion criteria			Х										
Confirm eligible APC			Х										
Confirm ED and ACU care available			Х										
Randomisation			Х										
Concomitant medication ^d		Х	Х										
Social determinants of health assessment		Х	Х								Х	Х	Х
EQ-5D-5L °		Х	Х								Х	Х	Х
Satisfaction with care questionnaire ^f		Х									Х	Х	Х
Vital signs ^g				Х	Х	Х	Х	Х	Х	Х	Х		
Pain score ^h				Х	Х	Х	Х	Х	Х	Х	Х	Х	Х
Protocol adherence ⁱ											Х		
Time to. disposition ^j											Х		
Time to readiness for discharge											Х		
Cumulative opiate dose k											Х		
Resource use CRF including Work Productivity and Activity Impairment Questionnaire ^m	r	х									х	x	х
APC episode resource use CRF											Х	Х	Х
Adverse events ⁿ											Х	Х	Х
Length of stay											Х		
Re-attendance												Х	Х
EQ-5D-5L for care givers		Х										Х	Х
Care giver questionnaire including Work Productivity and Activity Impairment Questionnaire		x										x	х

Abbreviations: ED; emergency department, ACU; ambulatory care unit, APC; acute painful crisis.

^a 6 hours, or until discharge if before

^b Age, sex, genotype

^cPast medical history, to include sickle complications

^d Collect information from the paper or electronic drug chart

^e Provide patient with the EQ-5D-5L questionnaire. To complete on presentation and 7 days after presentation.

^f Patient satisfaction questionnaire

^g Hourly for the first 6 hours a per standard of care. These results should be taken from the hospital paper or electronic record. Record actual values and percentage of scheduled measurement

^{*h*} Visual pain score to be taken by dedicated trial team. Score to be taken at baseline and hourly for the first 6 hours

^{*i*} Use the hospital or paper record to confirm adherence to protocol

^{*j*} Was the patient admitted or discharged from ED or ACU

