14.2 Source data

Source data worksheets will be supplied to all recruiting sites by the Trial Manager

The following Case Report Forms to be provided

Initial Consent

- Inclusion/Exclusion Criteria
- Background clinical data
- Usual analgesia protocol
- Date of continued consent
- QoL assessment with EQ-5D-5L
- Resource use CRF including Work Productivity and Activity Impairment
 Questionnaire

 Care giver questionnaire including Work Productivity and Activity Impairment Questionnaire

Presentation with APC

- Inclusion/Exclusion Criteria
- Baseline Clinical Assessment of APC
- QoL assessment with EQ-5D-5L (at presentation and at 6h)
- 1-6 hours Clinical Assessment
- 6-24 hours follow up Clinical Assessment
- APC episode resource use CRF (at end of episode at A&E or ACU)

Follow-up assessment 7-14 days after presentation

- SCAPE questionnaire
- QoL assessment with EQ-5D-5L
- Clinical Assessment
- (14d only) Resource use CRF including Work Productivity and Activity Impairment Questionnaire
- Care giver questionnaire including Work Productivity and Activity Impairment Questionnaire

Follow-up assessment at 28 days after presentation

- QoL assessment with EQ-5D-5L
- Resource use CRF including Work Productivity and Activity Impairment
 Questionnaire
- Care giver questionnaire including Work Productivity and Activity Impairment Questionnaire

SAE Form

CRF's will be in electronic format. Clinical information for the CRF's will be extracted from hospital paper and electronic records, and from study specific patient report forms.

Responsibility for completion of CRF's will be with delegated trial team members and will be supervised and monitored by the CI.

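### Sections 8 and 11.3.1 give randomised patients no EQ-5D-5L between 6 hours and day 14, so the 28-day QALY difference can be misstated in either direction; other sections point to earlier readings and must be reconciled

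*Protocol*

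**What the plan says.** Section 6.4 lists "QALY at 28 days post-randomisation" and an incremental cost-effectiveness ratio among the secondary endpoints. Section 11.3.1 (Assessment of outcomes) has the EQ-5D-5L "administered to patients at initial consent, at baseline, 6 hours, 14 days and 28 days follow up" and calculates QALYs "over follow-up periods using area under the curve approach". It does not say how utilities between readings are interpolated.

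Section 8 gives the same times for randomised patients: "Quality of life assessment; using the EQ-5D-5L tool taken on consent, presentation, 6 hours, 14 and 28 days after the presentation".

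Three other places differ:
- **Section 8, observational arm:** adds day 7, "using the EQ-5D-5L tool taken on consent, presentation, 6 hours and 7, 14 and 28 days after the presentation".
- **Section 9.6, Table 1:** the EQ-5D-5L row appears to be ticked at discharge as well as at days 14 and 28 (the table is broken in the text available). Its footnote reads "To complete on presentation and 7 days after presentation".
- **Section 14.2:** a follow-up visit dated 7 to 14 days after presentation includes the EQ-5D-5L. Only the resource-use form at that visit is restricted to day 14.

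Section 14.2 also has a form for a "6-24 hours follow up Clinical Assessment", but lists EQ-5D-5L around the episode only at presentation and 6 hours.

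**The concern.** On the Section 8 and 11.3.1 schedule, a trapezoidal area joins the 6-hour and day-14 utilities with one straight line. Whatever separates the arms at 6 hours is then credited as fading evenly over 13.75 days, and whatever separates them only within that interval is not seen.

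This interval matters because the rationale in Section 5.2 looks to admissions and bed days as places where ambulatory care may help. Section 11.3.1 adds that earlier studies of hospitalised patients "have shown a reduction in pain and an improvement in quality of life post treatment and discharge". Differences from being at home rather than in hospital would fall largely after 6 hours and before day 14.

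Cost-effectiveness is a stated secondary objective. The QALY difference is the denominator of the cost per QALY and also drives the reported probability of cost-effectiveness. Utilities that were never collected cannot be recovered by an analysis rule, so the schedule has to be settled before data collection.

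**Working it through.** The protocol gives no utility, QALY or recovery-time figure, so there is no figure of its own to reproduce.

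**Inputs from the protocol.** Readings after presentation at 0, 0.25, 14 and 28 days (Sections 8 and 11.3.1); area under the curve (11.3.1); 28-day horizon (6.4); thresholds up to £30,000 per QALY (Analysis of cost-effectiveness).

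**Assumptions.** Straight-line joining; no difference between arms at presentation or at day 14, except where recovery is exponential. The utility gap at 6 hours, the recovery times and the curve shapes are illustrative.

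**1. Weight of the 6-hour reading.** 0.25/2 + 13.75/2 = 0.125 + 6.875 = 7.0 days, and 7.0/28 = 25% of the horizon. The stretch without a reading is 13.75/28 = 49%.

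**2. A gap d at 6 hours that closes linearly on day R (up to 14).** Planned area = 7.0d. True area = 0.125d + (R − 0.25)d/2 = Rd/2. Ratio = 14/R. With a day-7 reading added and R no later than 7, the area is 0.125d + 6.75d/2 = 3.5d and the ratio is 7/R.

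| Gap closed on day | Planned / true | With day 7 | With days 1, 3 and 7 |
|---|---|---|---|
| 2 | 7.0 | 3.5 | 1.29 |
| 3 | 4.7 | 2.3 | 1.00 |
| 5 | 2.8 | 1.4 | 1.17 |
| 7 | 2.0 | 1.0 | 1.00 |
| 10 | 1.4 | 1.12 | 1.12 |
| 14 | 1.0 | 1.0 | 1.00 |

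**3. In QALYs, with d = 0.10.** Planned: 0.70/365.25 = 0.00192, or £57.5 at £30,000 per QALY. True if closed by day 2: 0.10/365.25 = 0.00027 (£8.2). True if closed by day 5: 0.25/365.25 = 0.00068 (£20.5).

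**4. Exponential recovery at the same rate in both arms** (6-hour utilities 0.4 and 0.5, plateau 0.8). The overstatement is 3.3 times for a time constant of 2 days, 2.3 for 3 days, 1.6 for 5 days and 1.3 for 7 days.

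**5. Equal utility at 6 hours (0.5), faster recovery to 0.8 in the ACU arm.** True gain = 0.3 × (difference in recovery day)/2. Day 2 against 4, and day 3 against 5: 0.30 utility-days each. Day 4 against 7: 0.45. The planned schedule gives 0 in all three, and so does the schedule with day 7 alone. With days 1, 3 and 7 the ratios are 1.11, 1.42 and 0.73.

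**6. Both effects together** (6-hour gap 0.10, same recovery pairs). True gains are 0.50, 0.55 and 0.80 utility-days against 0.70 planned, giving ratios of 1.40, 1.27 and 0.87. Day 7 alone gives 0.70, 0.64 and 0.44. Days 1, 3 and 7 give 1.15, 1.31 and 0.85.

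The effect of a discharge reading was not modelled.

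**The case against.** A reader might infer that the protocol collects nothing between 6 hours and day 14. It does not support that. Table 1 appears to tick discharge, which for a patient who stays in beyond 6 hours lies inside the interval. Its footnote and the 7-to-14-day visit point to day 7. This part of the objection stands: the firm documentary finding is an unreconciled schedule, and the gap exists only if Sections 8 and 11.3.1 prevail.

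A reader might also infer that crises resolve within days, so that the QALY difference is inflated several-fold. The protocol gives no recovery time, and Section 5.1 describes the length of episodes as unpredictable. The remark in Section 11.3.1 about improvement after discharge carries no timing. The ratios above run from zero, through about 1, to 7.0 according to what is assumed, and the two kinds of error can offset each other.

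The interpolation rule is unstated and a statistical analysis plan may supply it. Straight lines are only the natural reading, and length of stay and time to fitness for discharge could inform scenario analyses. That is fair, but any other rule would also be filling in an unmeasured stretch.

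The zero-gain case may be uncommon. Fitness for discharge in Section 6.4 depends on pain, mobility and observations, so an arm that avoids admissions may already differ at 6 hours.

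Finally, the sums are small: £57.5 − £8.2 = £49.3 per episode at the top threshold in the illustration. Nothing shows that a conclusion would change, and the planned cost per unit of pain reduction is untouched.

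**Conclusion.** The point holds in conditional form. If the times in Sections 8 and 11.3.1 are used and joined by straight lines, a quarter of the 28-day weight rests on the 6-hour reading regardless of recovery, and the difference between arms over the following 13.75 days is not observed. That weight follows from the schedule and the joining rule alone.

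The resulting error depends on assumed curves. It can be an overstatement of up to 7.0 times for a 6-hour gap closed by day 2, no error for one closed at day 14, or a complete miss of a gain confined to the interval. Trial data collected on that schedule could not show which case applied.

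The primary outcome is unaffected. The matter concerns a secondary endpoint, and it deserves correction because the remedy is cheap and mostly uses readings the protocol already contemplates.

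**What to change.** Reconcile Section 8 (both the randomised and observational lists), Table 1 with its footnote, Section 11.3.1 and Section 14.2 to one EQ-5D-5L schedule for randomised patients. It should include day 7 and, for those admitted, discharge. State that the area under the curve uses all readings at their actual times from presentation, and state the interpolation rule. Report the version that joins 6 hours directly to day 14 only as a sensitivity analysis.

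Preferably add one or two readings in days 1 to 3, by app or telephone. The existing 6-to-24-hour assessment form could carry one, and Section 11.1 already contemplates an app. Day 7 alone still leaves a 3.5-fold overstatement for a gap closed by day 2, misses gains complete before day 7, and in the mixed cases turns the estimate into an understatement. These extra readings are more open to debate than day 7 and discharge.

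The cost is a protocol and form amendment and a few more five-item questionnaires per episode, with slightly more participant burden and some missing early values.

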11.3.2 Assessment of costs

We will identify, measure and value costs across three broad categories.

a) Cost for the treatment of index acute painful crises

This will have two components: cost of treatment in ED or specialist centre and, if relevant, cost of hospitalisation. The first include medication and staff costs for index pain episode treatment and we will undertake a partial micro-costing to ensure consistency in the cost estimates between the two arms. We will cost pain treatment medications used using information on type and volume of medications used and applying national drug tariffs.²⁶ To estimate staff costs, we will collect data on the type and pay band of the professional providing treatment and duration of episode in ED or

ambulatory care for the index pain episodes extracted from hospital electronic systems. In a scenario analysis, we use established unit costs for pain episode treatment in ED, the national schedule unit costs of emergency care to these visits,²⁷ and in ambulatory units, the unit costs of treating patients for acute sickle cell pain under the current commissioning and reimbursement structure of specialised haemoglobinopathy services in the NHS.

The second component is hospitalisation cost. If patients are admitted after initially presenting at ED or ambulatory care unit for treatment of acute pain episode, we will cost these admissions using the case-mix-based reference costs for the respective admissions (HRGs based). For short admissions that do not require overnight stays, we will apply respective day case unit costs and for longer admissions, we will apply the unit cost of non-elective admitted care for sickle cell with crisis.

b) Cost of other health service use

In addition to index acute pain crises treatment costs, we will assess health care resource use and costs associated with outpatient, inpatient or emergency visits and services for sickle cell and, separately, non-sickle cell related health problems. We will consent patients and request linked routine Hospital Episode Statistics (HES) data,²⁸ including inpatient, outpatient, emergency care and critical care episodes for the 28 days period prior to index pain episode (baseline costs) and for the 28 days follow-up period in the study. We will report use of different categories of care and their cost by applying national tariffs to the service use data.

c) Lost productivity and informal care

We will complement the base-case evaluation from the NHS and PSS perspective with additional analysis from a societal perspective, which are highly relevant for SCD patients.^{29,30} To estimate non-health care costs of patients, caregivers and society, we will collect information on employment status, days out of work, time spent to travel and access care, mode of transport and how far they travelled for treatment, transport costs to access care for acute pain treatment, and informal care received. This data will be collected using study specific Case Report Form (CRF). We will integrate the Work Productivity and Activity Impairment (WAPI) Questionnaire³¹ to assess lost productivity and activity impairments.

Resource use data will be collected at consent, 14 and 28 days post randomisation covering resource use within the previous 14 days follow-up in the trial using this CRF.

Similarly, we will estimate and include costs from care givers' perspective. These include expenses incurred due to caring responsibility and the monetary value of the time they spend supporting and providing care to patients. For that purpose, we will develop a carer questionnaire that includes basic sociodemographic questions, employment information and WAPI version for care givers. We will then identify primary care providers, consent them and collect data at time points that align with patients.

